8.8. Follow-up of adverse events and serious adverse events and assessment of outcome

After the initial AE/SAE report, the investigator is required to proactively follow each patient and provide further information to the FDA on the patient’s condition.

All AEs and SAEs documented at a previous visit and designated as not recovered/not resolved or recovering/resolving will be reviewed at subsequent visits/contacts.

Investigators will follow-up patients:

- with SAEs or patients withdrawn from the study as a result of an AE, until the event has resolved, subsided, stabilized, disappeared, the event is otherwise explained, or the patient is lost to follow-up;
- or, in the case of other non-serious AEs, until they complete the study or they are lost to follow-up.

Clinically significant laboratory abnormalities will be followed up until they have returned to baseline, or a satisfactory explanation has been provided. Additional information (including but not limited to laboratory results) relative to the subsequent course of such an abnormality noted for any patient must be made available to the Study Monitor.

The outcome of any non-serious AE occurring within 30 days post-treatment administration (i.e., unsolicited AE) or any SAE reported during the entire study will be assessed as:

- Recovered/resolved
- Not recovered/not resolved
- Recovering/resolving
- Recovered with sequelae/resolved with sequelae
- Fatal (SAEs only).

8.9. Prompt reporting of serious adverse events

The paper SAE Report Forms and the facsimile (Fax) system will be the primary method for reporting SAEs during the study period.

8.9.1. Time frames for submitting serious adverse event reports to GSK Bio and Oncovir

SAEs (including any grade of pIMD) will be reported promptly to GSK Bio and Oncovir once the investigator determines that the event meets the protocol definition of an SAE. The investigator or designate will complete and submit relevant information on the SAEs in the paper SAE form **WITHIN 24 HOURS OF HIS/HER BECOMING AWARE OF THESE EVENTS**. Additional or follow-up information relating to the initial SAE report is also to be completed and submitted in the paper SAE form within 24 hours of receipt of such information.

GSK Biologicals and Oncovir may request that the investigator perform or arrange for the conduct of supplemental measurements and/or evaluations to elucidate as fully as possible the nature and/or causality of the AE or SAE.

[REDACTED]

[REDACTED]

[REDACTED]

[REDACTED]

[REDACTED]

24/24 hour and 7/7 day availability

8.9.2. Completion and transmission of serious adverse event reports to FDA

Once an investigator becomes aware that a SAE has occurred in a study patient (including a screened patient), the investigator or designate will complete and submit the information in the paper SAE form within 24 hours as outlined in Section 8.9.1. Submission of safety information to FDA will follow 21 CFR 312.32. The SAE form will always be completed as thoroughly as possible with all available details of the event and will be submitted by the investigator or designate. If the investigator or designate does not have all information regarding an SAE, he/she will not wait to receive additional information before notifying FDA of the event and completing the SAE forms. The SAE form should be updated when additional information is received and forwarded to FDA **WITHIN 24 HOURS** as outlined in Section 8.9.1.

The investigator will always provide an assessment of causality at the time of the initial report as described in Section 8.7.2.

For paper SAE Report Form the investigator or designate will report relevant information on SAEs to FDA within the 24 hours as outlined in Section 8.9.1. The SAE Report Form will

always be completed as thoroughly as possible with all available details of the event, signed by the investigator or designate, and forwarded to FDA within the designated time frames. If the investigator or designate does not have all information regarding an SAE, he/she will not wait to receive additional information before notifying FDA of the event and completing the form.

When additional information is received on a SAE after freezing of the patient's CRF, new or updated information is to be recorded on the paper SAE Report Form, with all changes signed and dated by the investigator. The updated SAE Report Form should be resent to FDA WITHIN 24 HOURS of receipt of the follow-up information as outlined in Section 8.9.1.

8.10. Regulatory reporting requirements for serious adverse events

The investigator, as the sponsor's representative will promptly report all SAEs to FDA in accordance with the procedures detailed in Section 8.9 and to GSK on a quarterly basis. The sponsor, MCC has a legal responsibility to promptly notify, as appropriate, both the local regulatory authority and other regulatory agencies about the safety of a product under clinical investigation. Prompt notification of SAEs by the investigator is essential so that legal obligations and ethical responsibilities towards the safety of other patients are met.

The investigator, or responsible person according to local requirements, will comply with the applicable local regulatory requirements related to the reporting of SAEs to the IRB/IEC and, if required, to the applicable government authority.

An investigator who receives an investigator safety report describing a SAE or other specific safety information (e.g., summary or listing of SAEs) from GSK Biologicals or Oncovir will file it with the respective Investigator Brochure or other appropriate study documentation and will notify the IRB or IEC, if appropriate according to local requirements.

8.11. Post-study adverse events and serious adverse events

A post-study AE/SAE is defined as any event that occurs outside of the AE/SAE detection period defined in Section 8.6. Investigators are not obligated to actively seek AEs or SAEs in former study participants.

However, if the investigator learns of any SAE, including a death, at any time after a patient has been discharged from the study, and (s)he considers the event reasonably related to the investigational product, the investigator will promptly notify the Study Contact for Reporting SAEs.

8.12. Pregnancy

Patients who become pregnant during the study treatment phase must not receive additional doses of study treatment but may continue other study procedures at the discretion of the investigator.

CONFIDENTIAL

The investigator or designate will collect pregnancy information on any patient who becomes pregnant while participating in this study, i.e., from signature of the first informed consent till the end of the 5-year follow-up period, or till recurrence/death if occurring before the end of the 5-year follow-up period. The investigator or designate will record pregnancy information on the Pregnancy Report Form and submit it to FDA, GSK Biologicals and Oncovir within 24 hours of learning of a patient's pregnancy. The patient will be followed to determine the outcome of the pregnancy. At the end of the pregnancy, whether that be full-term or prematurely, information on the status of the mother and child will be forwarded to GSK Biologicals and Oncovir. Generally, follow-up will be no longer than six to eight weeks following the estimated delivery date.

While pregnancy itself is not considered an AE or SAE, any pregnancy complication or elective termination of a pregnancy for medical reasons will be recorded as an AE or a SAE, as described in Sections 8.1 and 8.2, and will be followed as described in Section 8.6.

A spontaneous abortion is always considered to be a SAE and will be reported as described in Section 8.9. Furthermore, any SAE occurring as a result of a post-study pregnancy AND considered reasonably related in time to receipt of the investigational product by the investigator, will be reported to FDA as described in Section 8.9. While the investigator is not obliged to actively seek this information from former study participants, he/she may learn of a pregnancy through spontaneous reporting.

Information on pregnancies identified during the screening phase prior to treatment administration does not need to be collected; this information need not be communicated to safety.

8.13. Treatment of adverse events

Treatment of any adverse event is at the sole discretion of the investigator and according to current good medical practice. Any medications administered for the treatment of an AE should be recorded in the patient's CRF. Refer to Section 8.8.

9. PATIENT COMPLETION AND WITHDRAWAL

9.1. Patient completion of study treatment

A patient will be considered to have completed the study treatment when he/she has been under treatment until Month 27 and turns up for the concluding examination 30 months after the first administration of the study treatment.

Administration of the investigational treatment (recMAGE-A3 + AS15 ASCI +/- Poly IC:LC) should continue until completion, documented disease recurrence, withdrawal due to an unacceptable toxicity, or withdrawal for other reasons (see Section 9.2).

Once the patient has been withdrawn from the investigational treatment, the reason must be documented in the patient's medical records and CRF.

9.2. Patient withdrawal

Patients who are withdrawn because of AEs must be clearly distinguished from patients who are withdrawn for other reasons. Investigators will follow patients who are withdrawn as a result of a SAE/AE until resolution of the event (see Section 8.8).

Once a patient has been withdrawn, the reason must be documented in the patient's medical records and CRF.

Withdrawn patients will not be replaced.

9.2.1. Patient withdrawal from investigational product

A patient will be considered as being withdrawn from the investigational product when he/she does not receive any further planned dose after the date of withdrawal.

The investigator will document in the CRF whether the decision to discontinue further treatment was made by the patient or the investigator and which of the following possible reasons was responsible for withdrawal:

- (Serious) adverse event (including intercurrent illness, unacceptable toxicity)
- Disease recurrence
- Protocol violation
- Other (specify)

In case of withdrawal from the investigational product, the concluding visit will be performed as described in Section 6.3.9 and the patient will enter the follow-up phase with follow-up visits up to five years after first study dose. If the withdrawal from the study treatment is due to disease recurrence, the patient should be asked to come for the concluding visit but will not be asked to return for the six-monthly follow-up visits. The investigator will contact these patient once a year, e.g., by telephone, until 5 years after the first administration of the study treatment.

If the patient refuses or cannot undergo these study procedures, (s)he will be considered as withdrawn from the study (Section 9.2.2).

9.2.2. Patient withdrawal from the study

A patient will be considered as being withdrawn from the study when (s)he does not undergo any further planned study activity after the date of withdrawal.

CONFIDENTIAL

A patient may voluntarily discontinue participation in this study at any time. The investigator may also, at his/her discretion, discontinue the patient from participating in this study at any time. In addition, if the sponsor decides to discontinue the study, no further study procedures (including administration of the study treatment) will occur.

Information relative to the withdrawal will be documented on the Study Conclusion page of the CRF. The investigator will document whether the decision to withdraw from the study was made by the patient or the investigator and which of the following possible reasons was responsible for withdrawal:

- Death (any cause),
- (Serious) adverse event (including intercurrent illness, unacceptable toxicity),
- Disease recurrence,
- Consent withdrawal, not due to an adverse event,
- Lost to follow-up,
- Other (specify).

The investigator will contact these patients once a year, e.g., by telephone, until 5 years after the first administration of the study treatment.

9.3. Screen and baseline failures

A patient is considered to be a screen/baseline failure if the patient signs the first ICF but withdraws before receiving study treatment.

All patients having given consent to undergo MAGE-A3 expression screening and gene expression signature analysis upon resection of their tumor will be referenced into a screening section of the CRF.

10. STATISTICAL CONSIDERATIONS

10.1. Primary endpoints

Safety and Toxicity of the two regimens: adverse events and serious adverse events.

10.1.1. Safety and tolerability endpoints

Occurrence of adverse events up to 30 days after each study dose, including abnormal haematological and biochemical parameters.

Occurrence of serious adverse events and autoimmunity during the whole study duration (up to 30 days after the last administration of study treatment). For methods of analysis, see Section 10.7.5.

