6.3.7. Visit 5: Fifth study treatment administration

This visit will take place 12 weeks \pm 4 calendar days after the day of the first administration (Visit 1). Study procedures will be identical to those of Visit 3.

- For patients who agree, eight green tops of blood totaling 70 mL will be taken on days 1, 3, 7, 14 and 21 after the first and fifth doses of study drugs for assessment of T cell reactivity. Day 21 after the first dose of study drug would be the day of the second injection of study drug. Those assays will be performed by [REDACTED]

In addition:

- A CT scan of the neck, chest and upper abdomen and pelvic CT scans will be performed.
- Blood sampling for safety haematological and chemical assays (15 ml, as described in Section 6.4.2).
- A pregnancy test will be performed for females of childbearing potential. 6.3.8.
- Leukapheresis will be repeated.

Blood sampling for humoral immunity assays will be done (10 ml, as described in Section 6.4.2).

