6.3.8. Visits 6-13: Three-monthly maintenance treatment administrations

These visits will take place at 3-month intervals, i.e., at time-points 6, 9, ..., 27 months after Visit 1, with a permitted deviation from the scheduled time-point of up to 14 calendar days.

The following procedures will be performed at each of these visits:

- Physical examination (as at Visit 1, including ECOG performance status and disease assessment).
- A CT scan of the neck, chest and upper abdomen and pelvic CT scan.
- Before administration of study treatment the criteria for permanent stopping or postponement of study treatment (Sections 5.2.1.1 and 5.2.1.2) will be checked; if any of these is met, the patient will either be withdrawn from study treatment or the administration of study treatment will be postponed.
- Recording of (serious) adverse events and pIMD.
- A pregnancy test for females of childbearing potential.
- Recording of concomitant medications.
- Administration of the study treatment.

The following procedures will be performed before the administration of study treatment at Visits 7, 8 and 10:

- Blood samples (10 ml, as described in Section 6.4.2) for humoral immunity assays will be taken.

The following procedures will be performed once every year after Visit 1 (i.e. at Visits 8 and 12):

- Blood sampling (15 ml as described in Section 6.4.2) for haematological and chemical safety assays.

If any of the sixth to twelfth study treatment administrations had to be postponed (refer to Section 5.2.1.1 for criteria for postponement of study treatment), the subsequent Visit should be planned as close as possible to the 3-monthly interval of the original schedule, but with a minimum of 14 days between any two treatment administrations.

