6.4.5. Laboratory assays

Safety laboratory assays assessing the hematological parameters as well as renal and hepatic functions will be performed by the laboratory at the investigational site.

These assays (detailed in Table 8) will be performed before the first administration of the study treatment and then each year after Visit 1 until the end of the maintenance phase and at Visit 14 (Refer to Table 5 and Table 6). These parameters will not be recorded anymore during the follow-up phase (Table 7).

If a clinically significant abnormality in any laboratory parameter is detected at one of these assessments, it should be followed up as adequate until it has returned to normal or a satisfactory explanation has been provided. Refer to Section 8.5 for AE and SAE reporting.

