8.2. Definition of a serious adverse event

A serious adverse event (SAE) is any untoward medical occurrence that:

- a. Results in death,
- b. Is life-threatening,

NOTE: The term 'life-threatening' in the definition of 'serious' refers to an event in which the patient was at risk of death at the time of the event. It does not refer to an event, which hypothetically might have caused death, if it were more severe.

c. Requires hospitalization or prolongation of existing hospitalization,

NOTE: In general, hospitalization signifies that the patient has been detained (usually involving at least an overnight stay) at the hospital or emergency ward for observation and/or treatment that would not have been appropriate in the physician's office or outpatient setting. Complications that occur during hospitalization are AEs. If a complication prolongs hospitalization or fulfills any other serious criteria, the event is serious. When in doubt as to whether hospitalization occurred or was necessary, the AE should be considered serious.

Hospitalization for elective treatment of a pre-existing condition that did not worsen from baseline is not considered an AE.

d. Results in disability/incapacity, or

NOTE: The term disability means a substantial disruption of a person's ability to conduct normal life functions. This definition is not intended to include experiences of relatively minor medical significance such as uncomplicated headache, nausea, vomiting, diarrhea, influenza, and accidental trauma (e.g. sprained ankle) which may interfere or prevent everyday life functions but do not constitute a substantial disruption.

e. Is a congenital anomaly/birth defect in the offspring of a study patient.

f. Is a Grade 4 adverse event according to the Common Terminology Criteria for Adverse Events (CTCAE), Version 4.0 (cf. Appendix F)

Medical or scientific judgment should be exercised in deciding whether reporting is appropriate in other situations, such as important medical events that may not be immediately life-threatening or result in death or hospitalization but may jeopardize the patient or may require medical or surgical intervention to prevent one of the other outcomes listed in the above definition. These should also be considered serious.

Examples of such events are invasive or malignant cancers, intensive treatment in an emergency room or at home for allergic bronchospasm, blood dyscrasias or convulsions that do not result in hospitalization.

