In this study, Grade 3 autoimmune disorders according to the Common Terminology Criteria for Adverse Events (CTCAE), Version 4.0 (cf. Appendix F), will be considered as medically significant and will therefore be notified as SAE.

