10.7.5.1. Adverse events

Adverse events (AEs), including abnormal laboratory values, will be graded according to the CTCAE, Version 4.0 and coded to the preferred term (PT) level using the MedDRA dictionary.

The percentage of patients with adverse event(s) within 30 days of each recMAGE-A3 + AS15 ASCI dose +/- Poly IC:LC will be reported by treatment group with exact 95% confidence intervals, as per MedDRA terminology, by Preferred Term (PT) and System Organ Class (SOC), if appropriate. The same tabulation will be presented for grade 3, grade 4, related, grade 3 related and grade 4 related events, if appropriate.

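### Section 10.1.1 ends the primary SAE and autoimmunity endpoint 30 days after the last dose, although the protocol collects and summarises these events for longer

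*Combined protocol and SAP*

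**What the plan says.** **Endpoint.** Section 10.1.1 has two parts and refers to 10.7.5 for methods. The first is "Occurrence of adverse events up to 30 days after each study dose, including abnormal haematological and biochemical parameters". The second covers SAEs and autoimmunity "during the whole study duration (up to 30 days after the last administration of study treatment".

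**Collection.** Section 8.6 records AEs for 30 days after each dose. It records SAEs up to Visit 14 (Month 30), or up to 30 days after the last dose if treatment stops early. It records pIMD and autoimmune disease from Visit 1 to the end of follow-up. Section 3.2 and Table 7 follow SAEs related to study participation for 5 years from the first dose, and Table 7 also records pIMD at each follow-up visit.

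**Analysis.** Section 10.7.5.1 reports "The percentage of patients with adverse event(s) within 30 days of each recMAGE-A3 + AS15 ASCI dose", by preferred term. Section 10.7.5.2 summarises SAEs by arm with no end date. No subsection of 10.7.5 is devoted to pIMD.

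**What counts as serious.** Under 8.2 an event is serious if it "Is a Grade 4 adverse event according to the Common Terminology Criteria for Adverse Events (CTCAE), Version 4.0", and Grade 3 autoimmune disorders "will be considered as medically significant and will therefore be notified as SAE". Section 8.9.1 appears to count pIMD of any grade among SAEs, while 8.6 leaves each case to be recorded as an AE or an SAE.

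**Safety laboratory draws.** Visit 5 includes "Blood sampling for safety haematological and chemical assays (15 ml, as described in Section 6.4.2". For maintenance, 6.3.8 says "The following procedures will be performed once every year after Visit 1 (i.e. at Visits 8 and 12". A further draw is made at Visit 14. Section 6.4.5 describes the schedule as "then each year after Visit 1 until the end of the maintenance phase and at Visit 14 (Refer to Table 5 and Table 6".

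**The concern.** Section 10.1.1 defines a primary endpoint. If its parenthesis is applied literally, events that the CRF is designed to capture are left out of that endpoint. Two analysts working from the same database, one following 10.1.1 and one following 10.7.5.2, would report different SAE counts.

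Autoimmunity is the category most exposed. Section 8.3 lists pIMD as the event class of specific interest, and the trial adds a further TLR agonist to an already adjuvanted product. An autoimmune disease that first appears some months after the last dose is the kind of event long follow-up is meant to find, yet the primary endpoint stops well before that follow-up does.

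**Working it through.** The plan gives no figure to reproduce here, so the check compares windows and then counts days.

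**Step 1. The windows side by side**

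| Event | 10.1.1 endpoint ends | Collection ends | 10.7.5 analysis |
|---|---|---|---|
| Non-serious AE | 30 days after each dose | same (8.6) | same (10.7.5.1) |
| All SAEs, completers | last dose + 30 days | Visit 14 (8.6) | any time (10.7.5.2) |
| All SAEs, early discontinuation | last dose + 30 days | last dose + 30 days (8.6) | any time (10.7.5.2) |
| SAEs related to study participation | last dose + 30 days | 5 years (3.2, Table 7) | any time (10.7.5.2) |
| pIMD / autoimmune disease | last dose + 30 days | end of follow-up (8.6, Table 7) | serious: any time; non-serious: 30 days after each dose |

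The first row agrees throughout. The conflict lies in the SAE and pIMD rows.

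**Step 2. Days after the 10.1.1 cut-off**

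Inputs: Tables 5 and 6 put doses at weeks 0, 3, 6, 9, 12 and then every 12 weeks from 24 to 108, with Visit 14 at week 120 (28-day months).

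- Dose 13 is on day 108 × 7 = 756, so the cut-off is 756 + 30 = day 786.
- Visit 14 is on day 120 × 7 = 840. SAE gap in completers: 840 − 786 = **54 days**.
- With calendar months of 30.4375 days, dose 13 is on day 822, the cut-off is day 852 and Visit 14 is day 913. Gap: 913 − 852 = **61 days**.
- Early discontinuation: both windows end at last dose + 30 days, so the gap for SAEs in general is 0.
- pIMD and related SAEs, for a patient who completes 13 doses and stays relapse-free for 5 years (about 1,826 days): 1,826 − 786 = **1,040 days**, or 1,826 − 852 = **974 days** with calendar months.

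**Step 3. Non-serious pIMDs during treatment**

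The 30-day windows run without a break through induction (day 0 to 84 + 30 = 114) and then cover 30 days after each of 8 maintenance doses: 114 + 8 × 30 = 354 of 840 days (42%). The other 840 − 354 = 486 days are nine gaps of 84 − 30 = 54 days. The first eight gaps lie inside the 10.1.1 autoimmunity window, but a non-serious pIMD starting in them is still not in the 10.7.5.1 tabulation.

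**Step 4. Laboratory draws against the 30-day AE window**

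| Draw | Day | Previous dose (day) | Gap on schedule | Inside 30 days? |
|---|---|---|---|---|
| V5 | 84 | 4 (63) | 21 | yes |
| V8 | 336 | 7 (252) | 84 | not if drawn pre-dose |
| V12 | 672 | 11 (588) | 84 | not if drawn pre-dose |
| V14 | 840 | 13 (756) | 84 | no |

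Visit 14 is set from Visit 13 with 14 days' tolerance, giving 70 to 98 days, and no dose is given that day. It is outside the window for every patient who takes all 13 doses. V8 and V12 are dosing visits. Section 6.3.8 states pre-dose sampling for humoral blood but not for safety blood. If drawn after the dose, those values fall on day 0 of doses 8 and 12 and are inside. A postponed earlier dose (minimum spacing 14 days) could also bring them inside.

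Grade 4 laboratory values are SAEs. At Visit 14 they miss 10.1.1 (day 840 is after day 786) but enter 10.7.5.2. For lower grades, the worst-grade toxicity table in 10.3 states no window and may capture them. Whether they are recorded as AEs at all is unclear: 8.5 counts abnormalities after the start of therapy, while the N.B. in 8.6 restricts recording to its own time frame.

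**The case against.** The strongest reply is that little is lost. The AE window in 10.1.1 matches 8.6 and 10.7.5.1, and tying non-serious events to the 30 days after a dose is a legitimate choice. Safety is descriptive, with no test, threshold or power calculation. The synopsis and 10.1 name the safety endpoint without a window. Late SAEs are summarised under 10.7.5.2, and pIMDs, being AEs with listed preferred terms, can appear in 10.7.5.1 or in the 10.3 toxicity table. All of this stands, and it makes the fault one of definition and analysis, not of data capture. It does not remove the contradiction inside 10.1.1. Nor does it give non-serious pIMDs a place in 10.7.5 when they start more than 30 days after a dose. If 8.9.1 is read as making every pIMD an SAE, they reach 10.7.5.2, but 8.6 does not read that way.

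Three stronger readings are tempting and are not supported:

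- **Three of the four post-baseline laboratory draws are excluded.** Only V14 is outside without a condition, and only in patients who take all 13 doses. V8 and V12 depend on a draw time that the plan does not state.
- **More than half of pIMD follow-up across the trial is lost.** The 974 to 1,040 days apply only to a patient who completes treatment and stays relapse-free for 5 years. Section 6.3.10.2 follows safety in patients withdrawn from treatment only until another cancer treatment starts. Section 6.3.11 describes contacts after relapse as monitoring survival, although 8.6 has pIMD asked about at every contact. Deaths shorten observation further. No all-patient percentage can be fixed from the documents.
- **One arm is favoured.** Nothing in the documents gives a direction.

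It is also fair to say that this amendment is dated October 2015, while Appendix A expected recruitment to end by February 2013. Changing a primary endpoint definition late in an open-label trial has a cost.

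**Conclusion.** The SAE and autoimmunity window in 10.1.1 is wrong as written. It contradicts its own wording, the collection rules in 8.6, 3.2 and Table 7, and the analysis in 10.7.5.2.

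- Autoimmune events starting more than 30 days after the last dose are outside the primary endpoint in all patients.
- SAEs in general are outside for 54 to 61 days, in completers only. After early discontinuation, only pIMD and SAEs related to study participation are collected beyond the cut-off.
- Non-serious pIMDs starting more than 30 days after a dose are in no by-arm 10.7.5 analysis, taking 8.6's division into AE and SAE at its word.
- As a secondary point, non-serious laboratory abnormalities at Visit 14 are outside the AE window in patients who take all 13 doses. The same holds at V8 and V12 if blood is drawn pre-dose and on schedule.

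The day counts assume the scheduled visits and either 28-day or calendar months. The contradiction itself rests on no assumption.

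**What to change.** 1. In 10.1.1, replace the parenthesis: autoimmunity/pIMD to the end of follow-up; SAEs as in 8.6; SAEs related to study participation to 5 years as in 3.2. Reconcile this with 8.9.1 and 10.7.5.2. Report the count to last dose + 30 days beside it as the on-treatment view.
2. Add to 10.7.5 a by-arm pIMD table (any grade, serious and non-serious) with patient-years observed. Show events after the start of another anticancer treatment separately, or censor there in line with 6.3.10.2. State whether pIMD is asked about at annual contacts after relapse, because that sets the denominator.
3. Report the worst CTCAE laboratory grade by arm over all post-baseline results, taken from the recorded laboratory values, beside the within-30-days subset. Reconcile 8.5 with the N.B. in 8.6, and state whether safety blood at dosing visits is drawn before the dose.

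The cost is wording and two tables. No new samples are needed, since 8.5 and 8.6 already put laboratory results and pIMDs in the CRF. The downside is that a longer window takes in events less clearly tied to dosing and alters a primary endpoint definition late in an open-label trial. Keeping the 30-day view beside the longer one limits both.
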